6.6.7 Physical Examination

The physical examination results will be listed. Clinically relevant abnormalities will be summarized separately as medical history and/or adverse events.

6.6.8 Pregnancy Test

The pregnancy test results will be listed.

6.6.9 Prior and Concomitant Medications/Procedures

Verbatim descriptions of prior and concomitant medications and therapies will be mapped to the World Health Organization Drug Global version Q1 2022 or later.

Verbatim descriptions of concomitant procedures will be coded using version 25.0 or later of the Medical Dictionary for Regulatory Activities (MedDRA) with descriptions by System Organ Class (SOC), High Level Group Term, High-Level Term, Preferred Term, and Lower-Level Term.

A subject who reports multiple medications/procedures within the same Preferred Term (or SOC or ATC code) is counted only once for that Preferred Term (or SOC or ATC code) using the first occurrence chronologically.

Partial medication/procedure dates will be imputed the same way as adverse events dates for the purpose of distinguishing prior and concomitant medications/procedures. Prior medications/procedures are defined as medications/procedures with start date prior to the first dose of study medication. Concomitant medications/procedures are defined as medications/procedures with start date or end date after the first dose of study medication or are ongoing. Medications that start prior to first dose and continue post first dose are considered both prior and concomitant.

Prior and concomitant medications will be summarized separately by Anatomical-Therapeutic-Chemical classification (ATC) class (level 1) and preferred drug name.

Concomitant procedures will be listed. Based on sponsor review, concomitant anti-cancer surgeries and radiotherapy will be flagged in the listing.

6.6.10 ECOG PS

ECOG performance status shifts from Baseline to worst post baseline score will be summarized.

6.7 Pharmacokinetic Analysis

6.7.1 General Considerations

The PK Analysis Set will be used for PK analysis. Any protocol deviations (considered important protocol deviations) that could impact PK parameter estimates will be discussed with the Sponsor to determine whether any data or subject-level exclusions are necessary. All data that are excluded will be listed and the reason for exclusion clearly noted.

If a quantifiable pre-dose concentration of ZN-c5 or palbociclib or metabolites is detected and it represents no more than 5% of the C_{max} value following the first dose of this study, the subject's data will be included in the noncompartmental analysis (NCA), without adjustments. If the observed pre-dose value is greater than 5% of the C_{max} value following the first dose of this study, the subject's data will be excluded from NCA.

Actual sampling time points relative to dosing of each respective drug will be used for NCA, except for the pre-dose time points at Day 1 and Day 15, where the pre-dose time point will be set to 0. If the actual collection time is unknown, the nominal collection time will be used for the purposes of PK parameter estimation.

Concentration values that are below the lower limit of quantification (BQL) will be imputed as follows for NCA:

- BQL values at time points prior to any measurable concentrations for the first dose or at time points immediately prior to dosing for multiple dose will be imputed as 0.
- Any other BQL values will be set to missing.

The above rules should be applied separately for Cycle 1 Day 1 and Day 15 PK parameter estimations.

If there is insufficient amount of sample for the laboratory to report a concentration, then it will be treated as missing.

All PK concentration profiles will be summarized over time by visit, cohort, dosing regimen, and analyte in tabular and graphical formats and pharmacokinetic data will be presented in listings.

All concentration-time data and summary statistics will be reported to the same number of significant figures as displayed in the bioanalytical data, except for percentages, which will be reported to one decimal place.

All PK parameter estimates and summary statistics will be reported to 3 significant figures, with the exception of accumulation ratios (RAUC), metabolic ratios (MR), which will be reported to 3 decimal places, time-related parameters (including T_{last} , T_{max} , and $T_{1/2}$, which will be reported to two decimal places, and AUC_{extr} and $CV\%$ which will be reported to 1 decimal place.

6.7.2 Plasma Concentrations

The plasma concentrations of ZN-c5, palbociclib, and/or metabolites will be summarized using nominal sampling time by visit, cohort, dosing regimen (i.e. QD or BID), and analyte using descriptive statistics. A listing by subject of plasma concentrations and/or tumor concentrations of ZN-c5 (if available), sample collection times, and derived sampling time deviations will be provided.

Nominal sampling time points relative to dosing will be used for mean plots of concentration-time data. Actual sampling times will be used for individual concentration-time plots, including all recorded concentrations regardless of timing. BQL concentration values will be set to 0 for predose of Day 1, and set to a value equal to the LLOQ for all other time points for calculation of summary statistics and display. Summary statistics for concentration-time data will include n, mean, SD, arithmetic coefficient of variation (%), minimum, median, maximum, geometric mean, and geometric coefficient of variation (%).

The arithmetic and geometric means of plasma concentrations of ZN-c5, palbociclib, and metabolites, will be presented graphically on both linear and semi-logarithmic scales by visit, cohort, dosing regimen, and analyte. For individual profiles, figures will be presented for each subject with concentration-time profiles on both linear and semi-logarithmic scales. Concentration values of 0 will not be plotted in the semi-logarithmic plots. The following figures will be produced:

- Individual concentration versus actual time – linear scale (overlaid for each cohort)
- Individual concentration versus actual time – semi-log scale (overlaid for each cohort)
- Arithmetic Mean concentration versus nominal time – linear scale (overlaid for all cohorts)
- Arithmetic Mean concentration versus nominal time – semi-log scale (overlaid for all cohorts)
- Geometric Mean concentration versus nominal time – linear scale (overlaid for all cohorts)
- Geometric Mean concentration versus nominal time – semi-log scale (overlaid for all cohorts)

6.7.3 Pharmacokinetic Endpoints

The following PK parameters for ZN-c5, palbociclib, and metabolites will be estimated by NCA using the software Phoenix® WinNonlin® Version 8.3 (Certara, USA).

Table 5 Pharmacokinetic Parameters

PK Parameter	Definition
Cycle 1 Day 1	
Adjusted R ²	Adjusted coefficient of determination
AUC ₀₋₈	Area under the plasma concentration time curve from 0 to 8 hours post-dose
AUC ₀₋₁₂	Area under the concentration-time curve from the time of dosing to the end of the dosing interval (12 h post-dose for BID dosing; ZN-c5 only)
AUC ₀₋₂₄	Area under the concentration-time curve from the time of dosing to the end of the dosing interval (24 h post-dose for QD dosing)
AUC _{last}	Area under the plasma concentration-time curve from time 0 to time of last quantifiable plasma concentration
AUC _{inf}	Area under the plasma concentration-time curve from time 0 extrapolated to infinity
AUC _{extr}	The proportion of AUC _{0-∞} due to extrapolation from time T _{last} to infinity, expressed as a %
C _{max}	Maximum observed plasma concentration after a single dose administration
C ₀₋₁₂	Concentration at the end of the dosing interval (BID dosing; ZN-c5 only)
C ₀₋₂₄	Concentration at the end of the dosing interval QD dosing only)
T _{max}	Time of maximum observed plasma concentration after a single dose administration
λ _z	Terminal elimination phase rate constant
T _{1/2}	Apparent terminal elimination half life
T _{last}	Time of last observed quantifiable concentration
CL/F ^a	Apparent total plasma clearance after a single dose administration
V _z /F ^a	Apparent volume of distribution after a single dose oral administration
MR ^b	Metabolic ratio of the conversion of a parent drug to its metabolite using AUC ₀₋₁₂ or AUC ₀₋₂₄ as MR = AUC (metabolite)/AUC (parent), for BID dosing or QD dosing, as appropriate.
Cycle 1 Day 15	
Adjusted R ²	Adjusted coefficient of determination
AUC ₀₋₈	Area under the plasma concentration time curve from 0 to 8 hours post-dose
AUC _{tau}	Area under the concentration-time curve from the time of dosing to the end of the dosing interval (tau = 12 or 24 hours)
AUC ₀₋₂₄	Area under the concentration-time curve calculated as 2 × AUC ₀₋₁₂ for the BID dose only.
C _{max,ss}	Maximum observed plasma concentration after multiple dose administration
T _{max,ss}	Time of maximum observed plasma concentration after multiple dose administration
λ _z (Lambda z)	Terminal elimination phase rate constant

PK Parameter	Definition
T _{1/2}	Apparent terminal elimination half life
T _{last}	Time of last observable quantifiable concentration
C _{trough}	Concentration at the end of the dosing interval (tau = 12 or 24 hours)
C _{ave}	Average steady-state plasma concentration
CL _{ss} /F ^a	Apparent total plasma clearance after multiple dose oral administration
V _{z,ss} /F ^a	Apparent volume of distribution after multiple dose oral administration
MR ^b	Metabolic ratio of the conversion of a parent drug to its metabolite using AUC _{tau} as MR = AUC (metabolite)/AUC (parent), tau = 12 or 24 hours for BID dosing or QD dosing, respectively.
RAUC	AUC accumulation ratio defined as AUC Day 15/AUC Day 1 (where Day 1 AUC ₀₋₁₂ or AUC ₀₋₈ [BID dosing] or AUC ₀₋₂₄ [QD Dosing] and Day 15 AUC ₀₋₈ (BID dosing only) or AUC _{tau} ; tau = 12 (BID dosing) or 24 hours)

^a Determined for parent drug only

^b Determined for palbociclib and its metabolite

C_{max}, C_{max ss}, C₀₋₁₂, C₀₋₂₄, C_{trough}, T_{max}, and T_{max, ss} will be obtained directly from experimental observations. If multiple maxima occur at equal concentrations, the first temporal value will be taken as the C_{max}/C_{max ss} and T_{max}/T_{max, ss}.

T_{1/2}, where determinable, will be calculated as the natural logarithm of 2 divided by the terminal phase rate constant, lambda z (λ_z). The number of data points included in the regression will be determined by visual inspection, but a minimum of 3 data points in the terminal phase, excluding C_{max}/C_{max,ss}, is required to estimate λ_z . In addition, T_{1/2} should be determined with a span ≥ 2 with span defined as the time interval used to determine lambda z (i.e., upper lambda z minus lower lambda z) divided by the T_{1/2}. If this criteria is not met, the T_{1/2} data will be excluded from summary statistics but will listed and flagged.

In order for λ_z -derived parameters (λ_z , V_z/F, V_{ss}/F, and T_{1/2}) to be listed and summarized, the adjusted r² value reported in Phoenix®WinNonlin® must be ≥ 0.8 . In addition, AUC_{extr} must be <20% for Cycle 1 Day 1 PK parameters only (AUC_{inf}). All PK parameters that do not meet these criteria will be listed.

Regression parameters for estimation of λ_z , including the number of time points used, time point range, r-squared, adjusted r-squared, and span will be listed.

For the purpose of calculating AUC, all missing values will be treated as missing in the PK analysis and excluded from analysis except when they occur at pre-dose (of Day 1), where they will be set to 0. Missing pre-dose values for all other days will be handled on a case-by-case basis and may be imputed using the C_{trough} value for that corresponding dosing interval. If C_{trough} value is missing, the missing pre-dose will be imputed using the lowest concentration value observed for that corresponding dosing interval, if warranted.

All AUCs including partial AUCs (AUC₀₋₈, AUC₀₋₁₂, AUC₀₋₂₄, and AUC_{tau}) will be calculated using the linear trapezoidal method and actual elapsed time values. AUC₀₋₂₄ for the BID dosing will be determined by estimating $2 \times$ AUC₀₋₁₂ for Cycle 1 Day 15. If no PK sample was collected at the 12 or 24 hour post dose for either the BID or QD dosing regimen, one of two approaches will be taken to allow for the determination of AUC₀₋₈, AUC₀₋₁₂, AUC₀₋₂₄ or AUC_{tau}:

- For Cycle 1 Day 1, the 12 or 24 hour post-dose sample will be calculated via an extrapolation method using Phoenix® WinNonlin® standard calculations. If no lambda z is estimated, AUC₀₋₈, AUC₀₋₁₂ or AUC₀₋₂₄ will not be estimated. Moreover, the adjusted r^2 value must be ≥ 0.8 and AUC_{extr} must be <20% for AUC₀₋₈, AUC₀₋₁₂, and AUC₀₋₂₄ to be estimated by extrapolation.
- For Cycle 1 Day 15, the 12 or 24 hour post-dose sample will be imputed using the pre-dose concentration or the minimum observed concentration within that BID or QD dosing interval (if the pre-dose concentration is missing) to obtain the AUC_{tau}.

CL/F on Day 1 will be calculated as Dose (D)/AUC₀₋₁₂ or AUC₀₋₂₄ and CL_{ss}/F on Day 15 will be calculated as Dose (D)/AUC_{tau} (where tau = 12 or 24 hours).

V/F on Day 1 will be calculated as D/(λ * AUC₀₋₁₂ or AUC₀₋₂₄) and V_{z,ss}/F on Day 15 will be calculated as D/(λ * AUC_{tau}) (where tau = 12 or 24 hours).

C_{ave} will be calculated as AUC_{tau}/12 or AUC_{tau}/24 (where tau = 12 or 24 hours).

Plasma PK parameters (see [Table 5](#)) will be listed and summarized by cohort, analyte, and visit (Cycle 1 Day 1 or Cycle 1 Day 15) using descriptive statistics for the Safety Analysis Set and PK Analysis Set. Summary statistics for all other PK parameters include n, mean, SD, arithmetic coefficient of variation (%), median, minimum, maximum, geometric mean, and geometric coefficient of variation (%). Summary statistics for the PK parameters T_{max}, T_{1/2}, and T_{last} will include n, mean, SD, median, minimum, and maximum.

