6.1.4 MONOTHERAPY DOSE ESCALATION

In order to define an MTD or the RP2D for ZN-c5 as a single agent, this study will follow a standard 3+3 design. At least 3 and up to 6 evaluable subjects will be enrolled for each dose cohort. ZN-c5 will be administered orally once daily (alternatively, this total daily dose may be divided by 2 and administered BID [every 12 hours]), on a 28-day cycle (continuous dosing). The total number of patients will depend upon the number of dose escalations necessary, but it is estimated to be approximately 36 subjects.

Dose levels and dosing frequency may be adjusted during the study on the basis of emerging safety and PK data. Intermediate dose levels may be evaluated.

Additional subjects can be enrolled at a lower dose level already deemed well-tolerated; these patients will be part of the Monotherapy Expansion (Section 6.1.6).

At least 6 subjects will be treated at the MTD/RP2D.

The dose levels for the study are shown in Table 3.

Table 3: ZN-c5 Study Dose Levels

Dose Level*	ZN-c5* (once daily)**
1	50 mg
2	75 mg
3	100 mg
4	150 mg
5	300 mg
6	600 mg
7	900 mg
8	1200 mg

^{*}Dose Levels may be modified, and intermittent dose levels may be implemented based on emerging safety and PK results.

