6.5.6 Pharmacokinetic Variables

Plasma samples for ZN-c5 and its potential metabolites as applicable, and palbociclib (and metabolite) were collected as below. In case the dosing schedule was changed to BID dosing, an additional PK time point at 12 hours post ZN-c5 dosing was drawn (optional).

Day on Study	Time (hr)	Monotherapy	Combination Therapy	
		ZN-c5	ZN-c5	Palbociclib
Cycle 1 Day 1 and 15	T=0	PK (pre-dose, within 0.5 hrs)	PK (pre-dose, within 0.5 hrs)	NA
		Dose (fasted)	Dose (fasted)	NA
	0.5	PK	PK	NA
	1	PK	PK	NA
	2	PK	PK (prior to Palbociclib dosing)	PK (pre-dose, within 0.5 hrs)
				Dose (with food)
	2.5	NA	NA	PK (0.5-hr)
	3	NA	NA	PK (1-hr)
	4	PK	PK	PK (2-hr)
	6	PK	PK	PK (4-hr)
	8	PK	PK	PK (6-hr)
	10	NA	NA	PK (8-hr)
Cycle 1 Day 2 and 16	24	PK	PK	NA
	26	NA	NA	PK (24-hr)
Cycle 1 Day 8		PK (pre-dose, within 0.5 hrs)	PK (pre-dose, within 0.5 hrs)	PK
Cycle 2 Day 1		PK (pre-dose, within 0.5 hrs)	PK (pre-dose, within 0.5 hrs)	NA
Cycle 3 Day 1		PK (pre-dose, within 0.5 hrs)	PK (pre-dose, within 0.5 hrs)	NA
Cycle 4 Day 1		PK (pre-dose, within 0.5 hrs)	PK (pre-dose, within 0.5 hrs)	NA
NA= not applicable				

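### On the full PK grid, the linear trapezoid overstates reported once-daily ZN-c5 exposure relative to twice-daily, by an amount that depends on a half-life the documents do not give

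*SAP*

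**What the plan says.** SAP 6.7.3 (Pharmacokinetic Endpoints) sets one integration rule: AUCs, including AUC0-8, AUC0-12, AUC0-24 and AUCtau, "will be calculated using the linear trapezoidal method and actual elapsed time values". On Day 15, AUC0-24 "for the BID dosing will be determined by estimating" twice AUC0-12. CLss/F is dose divided by AUCtau, and Cave is AUCtau divided by 12 or 24.

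The full grid (SAP 6.5.6; Protocol 8.2.2.1, Table 6) samples ZN-c5 at 0, 0.5, 1, 2, 4, 6 and 8 hours on Days 1 and 15. The next sample is at 24 hours, in the row for "Cycle 1 Day 2 and 16". A 12-hour sample is added only under BID dosing, and it is optional.

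For a missing end-of-interval sample the rule differs by day. On Day 1, "the 12 or 24 hour post-dose sample will be calculated via an extrapolation method" based on lambda-z. On Day 15 it "will be imputed using the pre-dose concentration or the minimum observed concentration within that BID or QD dosing interval", the minimum being used only when the pre-dose value is missing.

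Protocol 6.1.4 states: "Dose levels and dosing frequency may be adjusted during the study on the basis of emerging safety and PK data". Protocol 6.1.7 lists PK among the inputs to Monotherapy Phase 2 dose selection and allows QD or BID doses there.

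**The concern.** Over a stretch of exponential decline, the chord between two sampled points lies above the curve, and the excess grows quickly with the length of the stretch. Here the length depends on the schedule: 16 hours for QD, 4 hours for BID. Two schedules with the same total daily dose and the same true daily exposure would therefore be reported with different AUC0-24, always with QD higher.

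The same AUCtau feeds Cave, CLss/F and Vz,ss/F, so those carry the error too. It is systematic, so it does not average out over subjects as random variability does. Doubling AUC0-12 puts BID on a 24-hour basis, and that is the figure a reader would naturally set beside the QD value. At stake is the accuracy of reported QD exposure and of any descriptive QD-versus-BID reading made from it.

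**Working it through.** The plan gives no figure for AUC error, half-life or QD/BID exposure ratio, so there is nothing of its own to reproduce.

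**Inputs.** From the documents: the linear rule and the doubling (SAP 6.7.3); QD times 0, 0.5, 1, 2, 4, 6, 8, 24 h and BID times 0, 0.5, 1, 2, 4, 6, 8, 12 h (SAP 6.5.6). Assumed, because not given: half-life 4 to 24 h and absorption rate ka 0.5 to 4 per hour.

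**Step 1, the last interval alone.** For mono-exponential decline with rate k = ln 2 / half-life over a gap T, linear/exact = (kT/2) × coth(kT/2). At a half-life of 8 h, k = 0.0866. For T = 16 h, kT/2 = 0.693 and coth = 1.667, giving 1.155. For T = 4 h, kT/2 = 0.173, giving 1.010. At other half-lives (QD vs BID): 4 h, 1.571 vs 1.040; 11 h, 1.083 vs 1.005; 24 h, 1.018 vs 1.001.

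**Step 2, the whole AUC at steady state.** One-compartment oral model, unit volume: C(t) = D·ka/(ka − k) × [e^(−kt)/(1 − e^(−k·tau)) − e^(−ka·t)/(1 − e^(−ka·tau))], with D = 1, tau = 24 for QD and D = 0.5, tau = 12 for BID. The true daily AUC is 1/k for both. Worked case, half-life 8 h and ka = 1 per hour:
- True AUC0-24 = 1/0.0866 = 11.54.
- QD, 8 to 24 h: C(8) = 0.625 and C(24) = 0.156. Linear 16 × (0.625 + 0.156)/2 = 6.25, exact 5.42.
- QD, 0 to 8 h: linear 6.06, exact 6.13.
- QD total 12.31, or +6.7%. Cave is also +6.7%; CLss/F is 1/1.067 = 0.937 of truth, or −6.3%.
- BID: 2 × 5.753 = 11.51, or −0.3%. QD/BID = 1.07 against a true 1.00.

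**Step 3, the range (ka 0.5 to 4 per hour).**

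| Half-life | QD/true | BID/true | QD/BID |
|---|---|---|---|
| 4 h | 1.13–1.17 | 0.996–1.000 | 1.14–1.17 |
| 6 h | 1.09–1.10 | 0.996–0.999 | 1.10–1.11 |
| 8 h | 1.06–1.07 | 0.996–0.998 | 1.07 |
| 11 h | 1.03–1.04 | 0.997–0.998 | 1.04 |
| 24 h | 1.006–1.009 | 0.998–0.999 | 1.01 |

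For ka between 0.7 and 2, the QD excess at 4 h is 14 to 16%.

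**Step 4, which half-lives the SAP would summarise.** SAP 6.7.3 admits a half-life to the summaries only if the lambda-z window spans at least two half-lives. The longest QD windows, from 1 or 2 h to 24 h, allow at most 23/2 = 11.5 h or 22/2 = 11 h. At 11 h the excess is about 4%, and it is larger for shorter half-lives.

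**Step 5, linear-up/log-down on the same samples.** In the one-compartment model QD/BID becomes 0.99 to 1.00 throughout. This model favours the log rule, because its decline is the shape that rule integrates exactly. In a harder case (half the AUC in a 2-hour phase, terminal half-life 8 to 36 h, ka 2), QD/BID is 1.07 to 1.10 with the linear rule and 1.03 to 1.05 with the log rule.

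**Step 6, missing samples and Day 1.** If the Day 15 BID 12-hour value is missing but pre-dose is present, pre-dose stands in; at steady state the two are equal and Step 2 holds. If both are missing, the interval minimum overstates BID by 0.4 to 7%; QD/BID then falls to 1.02–1.03 at 8 h and 0.99–1.00 at 16 to 48 h. Day 1 profiles with complete samples behave like Day 15 (ka 1: QD +15.5% at 4 h, +6.7% at 8 h, +0.6% at 24 h; BID −0.4% to −0.8%).

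**The case against.** The strongest objection is that the size cannot be fixed. With no human half-life in the documents, the one-compartment result runs from under 1% to about 17%, and Protocol 4.3 itself treats a Cmax change below 20% as small against exposure variability in patients. That stands as a limit on materiality. It does not cancel the point, because variability between subjects averages out in group summaries and a one-directional error does not.

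A reader might infer that dose or schedule selection was biased. The documents do not support this. The SAP is dated 17 February 2023 and the data cut-off in its Section 8 is 18 May 2022, so the rule governs how exposure is reported. Neither document says how AUC was computed when doses were chosen, and PK was one of several inputs. Nor is a QD-versus-BID AUC comparison planned: parameters are summarised by cohort, analyte and visit, and all analyses are descriptive (SAP 3.3, 6.7.3). Between QD doses with similar half-lives the error largely cancels.

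A reader might also extend the point to every AUC. AUC0-8 uses the same times under both schedules and has no differential error. A missing Day 1 end-of-interval value is extrapolated with lambda-z. Palbociclib has its own gap from 8 to 24 hours after dosing, but it is given once daily in every combination cohort, so no schedule contrast arises. Monotherapy Phase 2 uses by default the optional abbreviated grid (Day 15 pre-dose, 2 h and 4 h; Protocol Tables 5 and 7), which the 8-to-24 versus 8-to-12 hour contrast does not describe.

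**Conclusion.** The point holds as a minor reporting matter. On the full grid, QD AUC0-24 and AUCtau are overstated relative to BID, with Cave moving the same way and CLss/F the opposite way. Under one-compartment decline at steady state the QD excess is about 14 to 16% at a 4-hour half-life, 7% at 8 hours, 4% at 11 hours and 1% or less at 24 hours or longer, with BID within about 0.5%. These sizes rest on assumed half-lives and absorption rates, and on the BID 12-hour value being sampled or replaced by a steady-state pre-dose value. A long terminal half-life is not full reassurance if an earlier phase carries much of the AUC, as the biexponential case shows. The documents establish the direction and the mechanism; they do not establish that any past choice was affected.

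**What to change.** In SAP 6.7.3, replace the linear trapezoidal method with the linear-up/log-down trapezoidal method for AUC calculation. Add one sentence saying that the unsampled 8-to-24-hour interval under QD dosing limits any descriptive QD-versus-BID exposure comparison.

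The cost is one setting in the noncompartmental software and two short edits; no new samples or data are needed. SAP Section 4 places finalisation before database lock and analysis. There are two downsides. Reported QD AUCs become slightly smaller. And if decline is multi-exponential the log rule leaves part of the error (QD/BID 1.03 to 1.05 in the example above), which is why the limitation sentence is needed as well.

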	10	NA	NA	PK (8-hr)
Cycle 1	24	PK	PK	NA
Day 2 and 16	26	NA	NA	PK (24-hr)
Cycle 1 Day 8		PK (pre-dose, within 0.5 hrs)	PK (pre-dose, within 0.5 hrs)	РК
Cycle 2 Day 1		PK (pre-dose, within 0.5 hrs)	PK (pre-dose, within 0.5 hrs)	NA
Cycle 3 Day 1		PK (pre-dose, within 0.5 hrs)	PK (pre-dose, within 0.5 hrs)	NA
Cycle 4 Day 1		PK (pre-dose, within 0.5 hrs)	PK (pre-dose, within 0.5 hrs)	NA
NA= not applic	able	,	,	

In case the dosing schedule is changed to BID dosing, an additional PK time point at 12 hours post ZN-c5 dosing will be drawn (optional).

Table 7: Abbreviated Pharmacokinetic Sampling Time Points

Day of Study	Collection Time Points (and Allowable Windows)	ZN-c5	Palbociclib*
Cycle 1 Day	Pre-dose (within 0.5 hour prior to ZN-c5 administration)	Х	Х
15	2-hours (± 10 min) post ZN-c5 administration	Х	Х
	4-hours (± 1 hour) post ZN-c5 administration	Χ	Х
*in the combination parts of the study			

All efforts will be made to obtain the PK samples at the exact nominal time relative to dosing, however, samples obtained within 10% of nominal time from dosing are acceptable for up to and including the

12-hour time points. The 24-hour time points should be drawn within \pm 1 hour. A protocol deviation only applies if a PK time point is missed.

If the optional On-Treatment tumor biopsy is performed, an additional PK sample should be collected at that time, regardless if tissue was obtained for ZN-c5 tissue concentration.

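### In BID profiles without the optional 12 h sample, SAP 6.7.3 withholds Day 1 AUC0-8 for lack of a terminal slope it hardly needs, which biases the BID accumulation ratio downward

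*SAP*

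**What the plan says.** SAP Table 5 lists AUC0-8 on both Day 1 and Day 15 of Cycle 1 and defines it as "Area under the plasma concentration time curve from 0 to 8 hours post-dose". The same table defines RAUC as "AUC accumulation ratio defined as AUC Day 15/AUC Day 1". For BID dosing the Day 1 term may be AUC0-12 or AUC0-8, and the Day 15 term AUC0-8 or AUCtau. For QD dosing AUC0-8 plays no part in the ratio.

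The full sampling schedule (Protocol Table 6, SAP 6.5.6) has ZN-c5 samples at 0, 0.5, 1, 2, 4, 6 and 8 h after the dose. Both documents make the 12 h sample under BID optional.

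SAP 6.7.3 then sets a rule for incomplete profiles. Its trigger is "If no PK sample was collected at the 12 or 24 hour post dose for either the BID or QD dosing regimen". On Day 1 the terminal slope is used to extrapolate, with this consequence: "If no lambda z is estimated, AUC₀₋₈, AUC₀₋₁₂ or AUC₀₋₂₄ will not be estimated". The following sentence requires adjusted r2 of at least 0.8 and says that AUCextr "must be <20% for AUC₀₋₈, AUC₀₋₁₂, and AUC₀₋₂₄ to be estimated by extrapolation". On Day 15 the missing concentration is filled in from the pre-dose or lowest observed value, and no lambda z, r2 or AUCextr condition is set.

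A little earlier, the same section links the 20% limit on AUCextr to AUCinf.

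**The concern.** The trigger is a missing 12 h or 24 h sample. That gap has no bearing on an area that ends at 8 h. AUC0-8 is the natural fallback for RAUC when a BID profile has no 12 h sample, yet that is the situation in which the rule makes it conditional on a terminal slope and perhaps on extrapolation to infinity.

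The loss is not random. With sampling to 8 h, a longer half-life leaves more of the curve beyond the last sample. It also makes it harder to obtain a usable slope from at least three points after Cmax. The subjects most likely to lose their Day 1 denominator are those who accumulate most, while their Day 15 AUC0-8 remains. At stake is whether the reported BID accumulation of ZN-c5 is too low or, in small cohorts, missing.

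**Working it through.** The plan states no half-life, expected RAUC or sample size for this summary, so there is no figure to reproduce.

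**Inputs from the documents.** Sampling times as listed; dosing interval 12 h under BID; linear trapezoidal method; lambda z from at least three points after Cmax; adjusted r2 of at least 0.8; AUCextr below 20%.

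**Assumptions.** I read the 12 h sample in the trigger as belonging to BID and the 24 h sample to QD. The last usable BID sample is at 8 h, because the next-morning sample follows the evening dose. Kinetics are linear. No human half-life or absorption rate (ka) is given, so ranges are used.

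**Step 1. AUCextr limit, one compartment, instant absorption.**
- AUCextr = exp(-8k). Requiring less than 0.20 gives k > ln(5)/8 = 0.2012 per h, so the half-life must be below ln(2)/0.2012 = 3.45 h.
- RAUC = 1/(1 - exp(-12k)). At that limit it is 1/(1 - 0.0894) = 1.098.
- Half-lives of 4, 6, 8, 12 and 24 h give AUCextr of 25%, 40%, 50%, 63% and 79%, all above the limit. Their RAUC would be 1.14, 1.33, 1.55, 2.00 and 3.41.

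**Step 2. Oral absorption.** With the actual sampling times and ka from 0.5 to 3 per h, the longest half-life that passes is 1.98 to 3.27 h, where RAUC on AUC0-8 is 1.05 to 1.10. A worked case is ka = 1 per h and half-life 6 h (k = 0.1155):
- Total area 1/k = 8.66. Area beyond 8 h = 1.131 × (0.397/0.1155 - 0.0003) = 3.88. AUCextr = 3.88/8.66 = 45%.
- Day 1 AUC0-8 = 8.66 - 3.88 = 4.77.
- Steady-state AUC0-8 = 1.131 × [0.603/(0.1155 × 0.75) - 1.000] = 6.74.
- RAUC = 6.74/4.77 = 1.41, which would not be reported under the AUCextr limit.

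**Step 3. Simulation of both readings.** There were 4,000 BID subjects per row, none with a 12 h sample. Half-life and ka were lognormal with log-SD 0.4, median ka was 1.5 per h, and assay error was 10%. The slope was the best-fitting terminal segment, whereas the SAP uses visual inspection. Entries are the geometric mean RAUC on AUC0-8, with the share of subjects kept.

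| Median half-life (h) | All subjects | Lambda z condition only | Lambda z, r2 and AUCextr |
|---|---|---|---|
| 3 | 1.12 | 1.11 (96%) | 1.04 (52%) |
| 4 | 1.22 | 1.20 (93%) | 1.05 (27%) |
| 6 | 1.42 | 1.38 (82%) | 1.07 (5.7%) |
| 8 | 1.67 | 1.59 (75%) | 1.07 (1.3%) |
| 12 | 2.19 | 1.99 (57%) | 1.09 (0.05%) |
| 20 | 3.22 | 2.84 (37%) | none kept |

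Under lambda z alone the ratio is low by 1 - 1.38/1.42 = 3% at 6 h, 1 - 1.99/2.19 = 9% at 12 h and 1 - 2.84/3.22 = 12% at 20 h. With all conditions it is low by 1 - 1.07/1.42 = 25% at 6 h. Protocol Table 5 foresees about 6 to 12 full-PK subjects per dose level in the Monotherapy Expansion. If all were BID without a 12 h sample, 5.7% of them is 0.3 to 0.7 subjects, so the practical result could be a missing summary.

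**Step 4. Two-compartment check.** With a fast phase of 1 h and a slow phase of 12 or 24 h, a slope fitted over 4 to 8 h gives AUCextr of 0.9% to 12%, which passes. RAUC on AUC0-8 is then 1.04 to 1.41. The 1.10 ceiling is therefore a property of the one-compartment model.

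**The case against.** The strongest reply is that the r2 and AUCextr limits apply only to areas estimated by extrapolation, as their own sentence says. An AUC0-8 measured by trapezoids to 8 h is then exempt from them. This is a fair reading, and under it the bias is the modest one in the middle column. It does not rescue the lambda z sentence, which carries no such qualifier. Two programmers could follow the text and report different ratios.

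Three further points limit the harm:
- Day 1 AUClast has no lambda z condition. For a profile that ends at 8 h it is close to AUC0-8, so the information is largely recoverable. RAUC, however, is not defined on AUClast.
- AUCs use actual times, and draws within 10% of nominal are accepted, so an 8 h sample may fall at 7.2 h. With instant absorption and a half-life of 6 h, the missing 0.8 h is (0.435 - 0.397)/0.603, about 6% of AUC0-8. A short extension is enough for that; it does not call for a limit on extrapolation to infinity.
- RAUC is descriptive and is not among the PK parameters that the protocol names.

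A reader might infer more: that the BID ratio survives only in fast eliminators and shows almost no accumulation, or that the QD versus BID choice is compromised. The documents do not support this. BID subjects with a 12 h sample fall outside the rule and keep a ratio at any half-life, and nothing says how many lack that sample. The near-absence of accumulation needs the stricter reading and one-compartment kinetics. No section ties RAUC to a choice of schedule, and the SAP (17 February 2023) postdates the 18 May 2022 data cut-off.

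**Conclusion.** The concern holds in a limited form. For Day 1 BID profiles without the 12 h sample, SAP 6.7.3 withholds AUC0-8 when lambda z cannot be estimated. On the stricter reading it also does so when adjusted r2 is below 0.8 or AUCextr is 20% or more. Neither is warranted for a profile sampled to about 8 h. Because Day 15 has no matching condition, RAUC is lost preferentially in subjects with a long half-life and its summary is biased toward less accumulation.

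Under lambda z alone the simulated bias is about 3% at a median half-life of 6 h and 9% at 12 h. On the stricter reading, with one-compartment kinetics and a last sample at 8 h, only half-lives below about 3.4 h remain and RAUC cannot exceed about 1.10. Two-compartment profiles can pass with RAUC up to about 1.4. The half-life of ZN-c5 and the number of affected subjects are not stated, so these are ranges. The effect is confined to a descriptive PK summary for BID ZN-c5. The correction is still worth making, because the text is ambiguous and the repair is nearly free.

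**What to change.** In SAP 6.7.3:
- Delete AUC0-8 from both sentences of the Day 1 rule.
- State that AUC0-8 is calculated by the trapezoidal method whenever a quantifiable sample at about 8 h exists. If that sample was drawn slightly early, either allow the short extension to 8 h or use the same actual end time on both days.
- Keep the lambda z, r2 and AUCextr conditions only for AUC0-12 and AUC0-24 obtained by extrapolation.
- For BID profiles without a 12 h sample, define RAUC as Day 15 AUC0-8 divided by Day 1 AUC0-8.
- Report how many BID profiles lacked the 12 h sample and how many ratios are missing.

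The cost is a wording change and one programming condition. No new samples or data are needed.
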